4.4.2.6.1 OLE Phase

CDI12 analysis won't be repeated for the OLE phase since EDSS is only collected every 24 weeks post OLE Week 24.

4.4.2.7 Time to Onset of Confirmed Disability Progression for at Least 24 Weeks with the Initial Event of Neurological Worsening Occurring during the 96-Week, Double-Blind, Double-Dummy Treatment Period

This is the same as the 12-week confirmed disability progression, except that the confirmation of disability progression must occur at the regularly scheduled visit that is ≥ 24 weeks (≥ 161 days) after initial disability progression.

All initial disability progression events up to Week 96 with corresponding confirmation visits at the next schedule visit will be taken into account for the statistical analysis. The same analysis principles as described in Section 4.4.2.3 will be applied to the 24-week disability endpoint. The sensitivity analyses will be performed for the 24-week disability endpoint in the same way as for the 12-week endpoint.

Sample SAS code can be found below (SAS code is regarded as “draft” until fully validated at the analysis stage):

```
* Log-rank test;
proc lifetest data=CDP24;
  time CDP24TIME*CNSR(1);
  strata REGION BEDSSCAT / group=ARMCD;
  ods output HomTests =_logrank;
run;

* Cox regression model;
proc phreg data=CDP24;
  class ARMCD / descending;
```

```

model CDP24TIME*CNSR(1) = ARMCD / rl;
strata REGION BEDSSCAT;
ods output ParameterEstimates=est;
run;

```

4.4.2.7.1 OLE Phase

This analysis will be repeated to include EDSS assessments performed during the OLE period for the combined DB+OLE period, with the same baseline as for the analysis during DB.

Analysis containing only data from OLE will be performed considering the OLE baseline.

Moreover, the difference of survival curves will be analyzed every 24 weeks. Greenwood formula will be used to compute the corresponding 95% CI and p-value.

4.4.2.8 Total Number of New T1-Hypo-Intense Lesions (Chronic Black Holes) at Weeks 24, 48, and 96

The total number of new T1-hypo-intense lesions (chronic black holes) will be calculated as the sum of the individual number of new lesions at Weeks 24, 48, and 96. Data from other unscheduled assessments will not be included in this summary or analysis.

The same approach to analysis will be applied here as described in Section 4.4.2.4, with the following exception:

- Baseline covariates here will be as follows: treatment group, baseline T1-hypo-intense lesions count, baseline EDSS score (<4.0 vs. ≥ 4.0) and geographical region (United States vs. ROW).

Sample SAS code can be found below (SAS code is regarded as “draft” until fully validated at the analysis stage):

```

proc genmod data=MRICBH;
class ARMCD REGION BEDSSCAT;
model N MRICBH = ARMCD REGION BEDSSCAT BTILES /
offset=MRILOG link=log dist=negbin type3;
lsmeans ARMCD / exp cl;
ods output lsmeans=ls;
ods output ParameterEstimates=est;
run;

```

If the model fails to converge due to high number of zero chronic black hole counts, a logistic regression model will be performed on chronic black hole (present or not), adjusted for the same baseline variables. Patients withdrawn from treatment and having no chronic black holes: those withdrawn due to lack of efficacy or death are considered as having chronic black holes; otherwise, it will be considered a missing observation.

Note that the protocol and previous versions of this SAP did not make it clear that only new T1 hypo-intense lesions would be considered.

4.4.2.8.1 OLE Phase

This analysis will be modified to include data collected during the OLE period. This analysis will be an exploratory analysis and will be performed for each visit from baseline

up to the last mature visit. The last mature visit is defined as the visit where the majority of patients have completed prior to the data cutoff date. Of note, MRI is only collected once a year during OLE.

Adjusted rate and adjusted rate ratio based on the negative binomial models may not be estimable due to low number of lesions. Hence, unadjusted rate (total number of lesions divided by number of scans), unadjusted rate ratio and corresponding confidence intervals based on the exact poisson test will be presented.

4.4.2.9 Change in Multiple Sclerosis Functional Composite Scale Score from Baseline to Week 96

There are three primary measures in a MSFC score: 1) Timed 25-Foot walk; 2) 9-Hole Peg Test (9-HPT); and 3) Paced Auditory Serial Addition Test (PASAT-3 version). The MSFCS is based on the concept that scores for these three dimensions (arm, leg, and cognitive function) are combined to create a single score (the MSFC) that can be used to detect change over time in a group of patients with MS. Since the three primary measures differ in what they actually measure (time for the 9-HPT and 25-Foot Timed Walk, but number of correct answers for the PASAT-3), a common metric for these variables has been used to create a composite score for the three different measures. Z-score was selected for this purpose. The results from each of these three tests are transformed into Z-scores and averaged to yield a composite score for each patient at each timepoint.

$$\text{MSFC Score} = \{Z_{\text{arm, average}} + Z_{\text{leg, average}} + Z_{\text{cognitive}}\} / 3.0$$

Where Zxxx = Z-score

The following are MSFC components:

- Trial 1, Timed 25-Foot Walk
- Trial 2, Timed 25-Foot Walk
- Trial 1, Dominant Hand, 9-HPT
- Trial 2, Dominant Hand, 9-HPT
- Trial 1, Non-Dominant Hand, 9-HPT
- Trial 2, Non-Dominant Hand, 9-HPT
- PASAT-3

There are three derived results for three tests: 1) the average (reciprocal) scores from the four trials on the 9-HPT (the two trials for each hand are averaged, converted to the reciprocals of the mean times for each hand and then the two reciprocals are averaged); 2) the average scores of two 25-Foot Timed Walk trials; and 3) the number correct from the PASAT-3. The Z-score will be created for these three derived results to yield the composite score by the following formula.

Formula for Creating the MSFC Score to Compare Groups within a Study (The Preferred Method)

$$\text{MSFC Score} = \left\{ \left\{ \frac{\text{Average (1/9-HPT)} - \text{Baseline Mean (1/9-HPT)}}{\text{Baseline Std Dev (1/9 HPT)}} \right\} + \left\{ \frac{\text{Average 25-Foot Walk} - \text{Baseline Mean 25-Foot Walk}}{\text{Baseline Std-Dev 25-Foot Walk}} \right\} + \left\{ \frac{\text{PASAT-3} - \text{Baseline Mean PASAT-3}}{\text{Baseline Std Dev PASAT-3}} \right\} \right\} / 3.0$$

Note: "Average (1/9-HPT)" is the average of the inverse (reciprocal) for the mean time of the two trials on the right hand and reciprocal of the mean time of the two left-hand trials from the test patient; Baseline Mean (1/9-HPT) and Std Dev (1/9-HPT) are the baseline values from each patient in all study groups combined at the baseline assessment; "Average 25-Foot Walk" is the mean time from the two trials of the 25-foot timed walk; and we take the negative value of the Z-score to make the direction of change the same as the other components. Similarly, the Baseline Mean and Std Dev 25-Foot Walk are of all Baseline Groups combined; and "PASAT-3" is the score from the test patient, and the Baseline Mean PASAT-3 and Std Dev PASAT-3 of the combined baseline assessments. These are discussed below.

Note that changing the signs of the Z-scores for the 25-Foot Walk and using inverse value of 9-HPT to ensure that a negative value implies worsening, and a positive value implies improvement. More details can be found in the MSFC Manual.

- Missing data will be imputed as follows:
- For results within a given test:
 - 25-Foot Timed Walk trials: If the test results are not available due to a "physical limitation," impute the maximum possible value for the scale. If the test results are not available but it is NOT due to a "physical limitation," use the result from the other trial to impute the missing value.
 - 9-HPT: If the test results are not available due to a "physical limitation," impute the maximum possible value for the scale. If the test results are not available but it is NOT due to a "physical limitation," impute the missing test score using the result from the other trial of the same hand. If the result from the other trial of the same hand is also missing, use the average score from the other hand (or available score from one trial if the result from one trial only is available).
- For the composite score:
 - All available data will be used for analysis regardless of the timing of any protocol-defined relapse.

Outliers will be applied with the following rules:

- For 9-HPT, the lower bound is set to be 10 seconds ([Oxford Grice et al. 2003](#)), and the upper bound is set to be 300 seconds, according to the MSFC Manual.
- For 25-FWT, the lower bound is set to be 2.2 seconds ([Bohannon 1997](#)), and upper bound is set to be 180 seconds, according to the MSFC Manual.

- For PASAT, the lower and upper bounds are set to be 0 and 60 according to the MSFC Manual.
- For values outside the lower and upper bounds, they will be treated as missing, and the imputation rule applied as defined above.

The MSFC score will be summarized at baseline and at Weeks 12, 24, 36, 48, 60, 72, 84, and 96 using descriptive statistics for each treatment group. Data from other unscheduled assessments will not be included in this summary or analysis. The change from baseline to Weeks 12, 24, 36, 48, 60, 72, 84, and 96 in MSFC score will be computed and summarized using descriptive statistics for each treatment group.

For the assessment of differences in the mean change from baseline in MSFC score up to Week 96, a Mixed-Effect Model Repeated Measures analysis (MMRM) incorporating post-randomization data collected up to 96 weeks of treatment will be used to assess all data collected over time with consideration of the variance–covariance matrix of the repeated measures. This method allows for a general unstructured variance–covariance matrix and will include data from patients with incomplete data from some scheduled timepoints.

The model will be implemented in SAS using the MIXED procedure and will include the change from baseline in MSFC score as the dependent variable. The fixed effects in the model will include independent variables of randomized treatment, visit (nominal post \leq baseline visits as per the Schedule of Assessments) and treatment-by-visit interaction, along with the following baseline covariates: baseline MSFC score, baseline MSFC score by visit interaction, geographical region (United States vs. ROW), and baseline EDSS score (<4.0 vs ≥ 4.0). Visit will be treated as a repeated variable within a patient. Patient, treatment, and visit will be treated as factor variables. An unstructured variance–covariance structure will be applied to model the within-patient errors. The model will be fitted using the Restricted Maximum Likelihood method (REML). Denominator degrees of freedom will be estimated using Satterthwaite’s approximation.

To estimate the difference between the ocrelizumab and interferon beta-1a 44 μ g SC groups in mean change from baseline to Week 96, a treatment-by-visit interaction contrast will be constructed (i.e., the treatment group contrast at Week 96). On the basis of this analysis, least square means, standard errors, and the 95% confidence interval for the treatment difference will be reported.

Graphical presentations for least square means and 95% confidence intervals will be used to illustrate trends over time.

Sample SAS code can be found below (SAS code is regarded as “draft” until fully validated at the analysis stage):

```
proc mixed data=MSFCS method=REML;
  class REGION BEDSSCAT ARMCD VISIT USUBJID;
  model change = BFCS REGION BEDSSCAT ARMCD VISIT
```

```

BFCS*VISIT ARMCD*VISIT / ddfm= satterthwaite;
repeated VISIT / type=un subject = USUBJID;
lsmeans ARMCD*VISIT / pdiff cl;
ods output lsmeans = lsm; * contains the adjusted means;
ods output diffs = dif; * contains treatment differences;
run;

```

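### SAP 4.4.2.9 turns 9-HPT and walk times above the upper bound into missing values, so read literally a time just over the bound can score better than one just under it

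*SAP*

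**What the plan says.** SAP Section 4.4.2.9 gives ranges for the MSFC components. For the 9-HPT the lower bound is 10 s, "and the upper bound is set to be 300 seconds, according to the MSFC Manual". For the walk the lower bound is 2.2 s and the "upper bound is set to be 180 seconds, according to the MSFC Manual". PASAT runs from 0 to 60. One sentence then covers both ends of every range: "For values outside the lower and upper bounds, they will be treated as missing, and the imputation rule applied as defined above".

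The imputation rule it points back to has two branches.

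- **Result unavailable because of a physical limitation.** For both timed tests: "impute the maximum possible value for the scale".
- **Result unavailable for any other reason.** For the walk, "use the result from the other trial to impute the missing value". For the 9-HPT, "impute the missing test score using the result from the other trial of the same hand", and then: "If the result from the other trial of the same hand is also missing, use the average score from the other hand".

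The same section scores the 9-HPT as the average over the two hands of one divided by the mean time. It reverses the sign of the walk Z-score, so that a higher MSFC is better throughout. Sections 4.4.3.9 and 4.4.3.10 (walk and 9-HPT ratios to baseline) refer back to 4.4.2.9 for imputation. Sections 4.4.2.1 and 4.4.2.2 place MSFC change seventh among the secondary endpoints; it is confirmatory only if the earlier steps succeed. The SAP's amendment rationale lists handling of out-of-range MSFC values among the May 2015 additions.

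**The concern.** A time below the lower bound is implausible, and discarding it is reasonable. A time above the upper bound may be a genuine, very poor performance. The SAP accepts that a patient who cannot do the test should get the worst value. The out-of-range sentence works against that principle. A recorded time above the bound becomes missing because of its size, not because the site recorded a physical limitation, so on the literal wording it takes the second branch. It is then replaced by a result that was inside the range, which is at least as good as the bound and usually much better.

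At stake is the ordering of the score. A patient whose hand slows from 295 s to 310 s should not move up. The rule can remove recorded poor performance from an endpoint that may be tested in a confirmatory manner, and the imputation step is shared with two exploratory analyses.

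**Working it through.** **Inputs from SAP 4.4.2.9.** The bounds, the two imputation branches and the scoring formula given above.

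**Assumptions.** (a) The maximum possible value in the physical-limitation branch is taken as 300 s for the 9-HPT and 180 s for the walk; the SAP gives no separate figure. (b) The baseline SD of the mean reciprocal is taken as 0.008 to 0.012 per second; the SAP gives none.

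The plan states no figure to reproduce here, so the check applies the rule as written to example patients.

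**1. 9-HPT, good hand 25 s on both trials, other hand as shown.** Arm score = (1/25 + 1/t)/2.

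| Other hand | t used | Arm score |
|---|---|---|
| 295 s and 295 s | 295 | (0.0400 + 0.0034)/2 = 0.0217 |
| recorded as unable | 300 | (0.0400 + 0.0033)/2 = 0.0217 |
| 310 s and 310 s, rule as written | 25 (other hand copied) | (0.0400 + 0.0400)/2 = 0.0400 |

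The gap between the last two rows is 0.0400 − 0.0217 = 0.0183. Dividing by the assumed SD gives 0.0183/0.012 = 1.5 to 0.0183/0.008 = 2.3 Z units on the arm component. Dividing by 3 for the composite gives 0.5 to 0.8 MSFC points.

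**2. 9-HPT, one trial over the bound.** Good hand 25 s, other hand 200 s and 310 s. The rule copies 200 s: (1/25 + 1/200)/2 = 0.0225. With the second trial recorded as unable, the hand mean is (200 + 300)/2 = 250 s and the score is (1/25 + 1/250)/2 = 0.0220. The direction is the same, but the gap is small.

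**3. Walk, one trial over the bound.** Trials of 60 s and 185 s score 60 s. If the second trial took 179 s, the mean is (60 + 179)/2 = 119.5 s; if it was recorded as unable, (60 + 180)/2 = 120 s. With a more consistent pair, 170 s and 185 s, the rule gives 170 s against (170 + 180)/2 = 175 s.

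**4. Is the ordering general for one hand?** With one trial over 300 s, the partner trial was set to every whole second from 10 to 300 (291 values). The over-bound hand never scored worse than the hand with that trial recorded as unable; the only tie was at 300 s.

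**5. Nothing left to copy.** If both walk trials exceed 180 s, or all four peg trials exceed 300 s, there is no in-range trial to borrow. The component is missing, whereas a patient recorded as unable gets 180 s or 1/300. The composite formula needs all three components, and the section gives no fallback.

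**The case against.** **The times may be data errors.** The bounds are attributed to the MSFC Manual, which is not part of these documents. If 300 s and 180 s are the longest times the tests allow, a larger number may be a recording error, and discarding it is defensible. This stands in part: a gross error should be queried, not scored. It does not rescue the rule, which makes no distinction and hands every over-limit time a replacement inside the range.

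**The branch is inferred.** The SAP does not say how an over-limit attempt is classified. If it counts as a physical limitation, the worst value is imputed and the problem goes away. That is true, but nothing in the SAP says so, and the literal wording leads to the other branch.

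**A reader might infer that the slowest patients in general score better.** The documents do not support that. Borrowing from the other hand exists only for the 9-HPT, and only when both trials of a hand are out of range; the walk can borrow only from its other trial. Patients over the bound on every trial have no component score at all.

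**A reader might also infer that the rule biases the MSFC comparison in favour of ocrelizumab, or upward in general.** This is not shown. The endpoint is change from baseline, and the rule carries no visit restriction. An over-bound baseline value would also be improved, which makes later change look worse. The rule is the same in both arms. For scale, 0.8 points in one of about 400 patients per arm moves that arm's raw mean by 0.8/400 = 0.002.

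**Conclusion.** The concern holds as a defect in the scoring rule. Read literally, Section 4.4.2.9 makes the timed components non-monotone: a time above the bound can score better than one just below it, and better than a recorded inability. When no in-range trial remains, the result disappears from that visit.

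The direction for an affected 9-HPT or walk component follows from the SAP's wording, provided the value is not also classed as a physical limitation. The 0.5 to 0.8 points belong to one constructed patient and rest on the assumed SD and on 300 s as the maximum. Times this long are probably rare with entry EDSS limited to 0–5.5 at screening, but the documents give no frequency. Neither the direction nor the size of any effect on the treatment contrast is established. This is a minor point, worth settling because the repair is simple.

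**What to change.** In SAP 4.4.2.9, after querying suspected entry errors, set values above the upper bound equal to that bound: 300 s for the 9-HPT and 180 s for the walk. Say that these are the maximum values meant in the physical-limitation rule. Keep treatment as missing for times below the lower bound and for PASAT outside 0–60. Capping also covers the case where every trial is over the bound.

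Carry the same wording into Sections 4.4.3.9 and 4.4.3.10. They refer to 4.4.2.9 for imputation but do not say whether its bounds apply.

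Section 2.4 lists the primary CSR as completed, so for the existing results report how many 9-HPT and walk values exceeded the bounds, by arm and visit, and how they were handled. Then rerun the MSFC analysis with capping as a sensitivity analysis.

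The cost is a sentence in the section, a small change to the derivation code, matching wording in the two ratio sections, and a small re-analysis that is necessarily post-unblinding and should be labelled so. The downside is that an entry error which escapes query would be scored as the worst value.

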4.4.2.9.1 OLE Phase

This analysis won't be repeated for the OLE phase as this data is not being collected during the OLE phase.

4.4.2.10 Percentage Change in Brain Volume as Detected by Brain Magnetic Resonance Imaging Scan from Week 24 to Week 96

Brain volume is recorded as an absolute “normalized” value at the baseline visit then recorded at subsequent visits as a percentage change relative to the absolute value at the baseline visit. Therefore, brain volume at Week 24 will be calculated as the brain volume at the baseline visit multiplied by $1 + ([\text{percentage change in brain volume from baseline visit to Week 24}]/100)$. This value will be used to determine the percentage change in brain volume at Weeks 48 and 96 relative to Week 24.

Percentage change in brain volume relative to Week 24, as detected by brain MRI scan, will be computed and summarized at Weeks 48 and 96 using descriptive statistics for each treatment group. Data from other unscheduled assessments will not be included in this summary or analysis.

For the assessment of differences in the mean percentage change in brain volume on MRI scans from Week 24 to Week 96, an MMRM analysis will be undertaken using the same approach as described in Section 4.4.2.9, except for the following:

- The response variable will be the percentage change from Week 24 to subsequent visits (Weeks 48 and 96). Baseline brain volume data will not feature in this analysis.
- Baseline covariates here will be as follows: brain volume at Week 24, geographical region (United States vs. ROW), and baseline EDSS score (<4.0 vs ≥ 4.0)
- To estimate the difference between the ocrelizumab and interferon beta-1a 44 µg SC groups in mean change from Week 24 to Week 96, a treatment-by-visit interaction contrast will be constructed (i.e., the treatment group contrast at Week 96)

Sample SAS code can be found below (SAS code is regarded as “draft” until fully validated at the analysis stage):

```

proc mixed data=MRINBV method=REML;
class REGION BEDSSCAT ARMCD VISIT USUBJID;
model change = W24NBV REGION BEDSSCAT ARMCD VISIT
W24NBV*VISIT ARMCD*VISIT / ddfm= satterthwaite;
repeated VISIT / type=un subject = USUBJID;
lsmeans ARMCD*VISIT / pdiff cl;
ods output lsmeans = lsm; * contains the adjusted means;
ods output diffs = dif; * contains treatment differences;
run;

```

The choice of Week 24 as “baseline” in this analysis, rather than the baseline visit, is a widely accepted approach to establish a stable baseline and avoid the effect of pseudoatrophy commonly reported for immunomodulatory therapies.

